## 9 Study Management

### 9.1 Pre-study Documentation

This study will be conducted in accordance with the ethical principles that have their origin in the Declaration of Helsinki as stated in 21 CFR §312.120(c)(4); consistent with GCP and all applicable regulatory requirements.

Before initiating this trial, the Investigator will have written and dated approval from the Institutional Review Board for the protocol, written informed consent form, subject recruitment materials, and any other written information to be provided to subjects before any protocol related procedures are performed on any subjects.

The clinical investigation will not begin until either FDA has determined that the study under the Investigational Drug Application (IND) is allowed to proceed or the Investigator has received a letter from FDA stating that the study is exempt from IND requirements.

The Investigator must comply with the applicable regulations in Title 21 of the Code of Federal Regulations (21 CFR §50, §54, and §312), GCP/ICH guidelines, and all applicable regulatory requirements. The IRB must comply with the regulations in 21 CFR §56 and applicable regulatory requirements.

### 9.2 Institutional Review Board Approval

The protocol, the proposed informed consent form, and all forms of participant information related to the study (e.g., advertisements used to recruit participants) will be reviewed and approved by

the UCSF Institutional Review Board. Prior to obtaining IRB approval, the protocol must be approved by the Helen Diller Family Comprehensive Cancer Center Site Committee and by the Protocol Review Committee (PRC). The initial protocol and all protocol amendments must be approved by the IRB prior to implementation.

### **9.3 Informed Consent**

All participants must be provided a consent form describing the study with sufficient information for each participant to make an informed decision regarding their participation. Participants must sign the IRB-approved informed consent form prior to participation in any study specific procedure. The participant must receive a copy of the signed and dated consent document. The original signed copy of the consent document must be retained in the medical record or research file.

### **9.4 Changes in the Protocol**

Once the protocol has been approved by the UCSF IRB, any changes to the protocol must be documented in the form of an amendment. The amendment must be signed by the Investigator and approved by PRC and the IRB prior to implementation.

If it becomes necessary to alter the protocol to eliminate an immediate hazard to patients, an amendment may be implemented prior to IRB approval. In this circumstance, however, the Investigator must then notify the IRB in writing within five (5) working days after implementation. The Study Chair and the UCSF study team will be responsible for updating any participating sites.

### **9.5 Handling and Documentation of Clinical Supplies**

The UCSF Principal Investigator and each participating site will maintain complete records showing the receipt, dispensation, return, or other disposition of all investigational drugs. The date, quantity and batch or code number of the drug, and the identification of patients to whom study drug has been dispensed by patient number and initials will be included. The sponsor-investigator will maintain written records of any disposition of the study drug.

The Principal Investigator shall not make the investigational drug available to any individuals other than to qualified study patients. Furthermore, the Principal Investigator will not allow the investigational drug to be used in any manner other than that specified in this protocol.

### **9.6 Case Report Forms (CRFs)**

The Principal Investigator and/or his/her designee will prepare and maintain adequate and accurate participant case histories with observations and data pertinent to the study. Study specific Case Report Forms (CRFs) will document safety and treatment outcomes for safety monitoring and data analysis. All study data will be entered into OnCore® via standardized CRFs in accordance with the CTMS study calendar, using single data entry with a secure access account. The Clinical Research Coordinator (CRC) will complete the CRFs as soon as possible upon completion of the study visit; the Investigator will review and approve the completed CRFs.

The information collected on CRFs shall be identical to that appearing in original source documents. Source documents will be found in the patient's medical records maintained by UCSF personnel. All source documentation should be kept in separate research folders for each patient.

In accordance with federal regulations, the Investigator is responsible for the accuracy and authenticity of all clinical and laboratory data entered onto CRFs. The PI will approve all completed CRFs to attest that the information contained on the CRFs is true and accurate.

All source documentation and CTMS data will be available for review/monitoring by the UCSF DSMC and regulatory agencies.

The Principal Investigator will be responsible for ensuring the accurate capture of study data. At study completion, when the CRFs have been declared to be complete and accurate, the database will be locked. Any changes to the data entered into the CRFs after that time can only be made by joint written agreement among the Study Chair, the Trial Statistician, and the Protocol Project Manager.

## **9.7 Oversight and Monitoring Plan**

The UCSF Helen Diller Family Comprehensive Cancer Center DSMC will be the monitoring entity for this study. The UCSF DSMC will monitor the study in accordance with the NCI-approved Data and Safety Monitoring Plan (DSMP). The DSMC will routinely review all adverse events and suspected adverse reactions considered "serious". The DSMC will audit study-related activities to ensure that the study is conducted in accordance with the protocol, local standard operating procedures, FDA regulations, and Good Clinical Practice (GCP). Significant results of the DSMC audit will be communicated to the IRB and the appropriate regulatory authorities at the time of continuing review, or in an expedited fashion, as applicable. See Appendix 3 Data and Safety Monitoring Plan for a Phase 2 or 3 Institutional Study, for additional information.

## **9.8 Record Keeping and Record Retention**

The Principal Investigator is required to maintain adequate records of the disposition of the drug, including dates, quantity, and use by subjects, as well as written records of the disposition of the drug when the study ends.

The Principal Investigator is required to prepare and maintain adequate and accurate case histories that record all observations and other data pertinent to the investigation on each individual administered the investigational drug or employed as a control in the investigation. Case histories include the case report forms and supporting data (e.g., signed and dated consent forms and medical records, such as progress notes of the physician, the individual's hospital chart(s), and the nurses' notes. The case history for each individual shall document that informed consent was obtained prior to participation in the study.

Study documentation includes all CRFs, data correction forms or queries, source documents, Sponsor-Investigator correspondence, monitoring logs/letters, and regulatory documents (e.g., protocol and amendments, IRB correspondence and approval, signed patient consent forms).

Source documents include all recordings of observations or notations of clinical activities and all reports and records necessary for the evaluation and reconstruction of the clinical research study.

In accordance with FDA regulations, the investigator shall retain records for a period of 2 years following the date a marketing application is approved for the drug for the indication for which it is being investigated; or, if no application is to be filed or if the application is not approved for such indication, until 2 years after the investigation is discontinued and FDA is notified.

## Appendix 1 Schedule of Study Procedures and Assessments

Trial Period:	Screening Phase a	Treatment Cycles b								End of Treatment e	Post-Treatment Follow-up f
						To be repeated beyond 8 cycles					
Treatment Cycle/Title:	Main Study Screening	1	2	3	4	5	6	7	8	End of Treatment (EOT) visit	Safety Follow-up Visit
		-28 to -1	± 3	± 3	± 3	± 3	± 3	± 3	± 3		30 days post discon
Administrative Procedures											
Informed Consent	X										
Inclusion/Exclusion Criteria	X										
Demographics and Medical History	X										
Prior and Concomitant Medication Review	X										
Post-study anticancer therapy status										X	X
Survival Status										X	X
Trial Treatment Administration											
Ipilimumab		X	X	X	X						
Pembrolizumab		X	X	X	X	X	X	X	X		
Aspirin		X	X	X	X	X	X	X	X		
Clinical Procedures/Assessments											
Review Adverse Events		X	X	X	X	X	X	X	X		X
Full Physical Examination	X	X	X	X	X	X	X	X	X		X
Vital Signs and Weight	X	X	X	X	X	X	X	X	X		X
ECOG Performance Status	X	X	X	X	X	X	X	X	X		X
Laboratory Procedures/Assessments											
Pregnancy Test – Urine or Serum-HCG c	X										
PT/INR and aPTT	X										
CBC with Differential	X	X	X	X	X	X	X	X	X		
Comprehensive Serum Chemistry Panel	X	X	X	X	X	X	X	X	X		
Urinalysis	X										
T3, FT4 and TSH	X	X	X	X	X	X	X	X	X		
Tumor Tissue Collection g	X										
Efficacy Measurements											
Tumor Imaging d	X				X				X		

a. Screening procedures to be completed within 28 days of C1D1, except laboratory tests for screening should be performed within 10 days prior to the first dose of treatment.

- b. Patients will take aspirin daily and receive pembrolizumab and ipilimumab every 3 weeks for 4 cycles. After 4 cycles, ipilimumab will be discontinued and patients will continue receiving pembrolizumab every 3 weeks while taking aspirin daily.
- c. Women of childbearing potential: negative urine or serum pregnancy test within 72 hours prior to receiving trial treatment. If urine test is positive or non-confirmatory, a serum pregnancy test will be required.
- d. Prefer imaging of chest/abdomen and pelvis. PET/CT, CT, or MRI are acceptable.
- e. End of Treatment (EOT) is defined as date patient and/or treating physician decides to discontinue study treatment. EOT visit and enter the post-treatment (follow-up) period. EOT visit should occur within 30 days of last dose of study drug or the decision to discontinue study drug. If a patient discontinues study drug at a scheduled visit, the EOT visit can occur the same day. The EOT assessments do not need to be repeated if done within the preceding 14 days. The EOT visit can be combined with a safety follow-up visit.
- f. Safety follow-up can be combined with the EOT visit.
- g. If available, archival tissue samples will be collected at screening and processed for PD-L1 expression testing. FFPE blocks will be requested from specimens containing melanoma tissue and 5 slides of 5 $\mu$ M thickness will be cut from each block. The unstained slides will be shipped to Qualtek for staining with the 22C3 antibody. The stained samples will be graded according to MEL score.

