## Metastatic Melanoma

In patients receiving ipilimumab 3 mg/kg in Trial 1, severe to life-threatening immune-mediated endocrinopathies (requiring hospitalization, urgent medical intervention, or interfering with activities of daily living; Grade 3 to 4) occurred in 9 ipilimumab-treated patients (1.8%). All 9 patients had hypopituitarism and some had additional concomitant endocrinopathies such as adrenal insufficiency, hypogonadism, and hypothyroidism. Six of the 9 patients were hospitalized for severe endocrinopathies. Moderate endocrinopathy (requiring hormone replacement or medical intervention; Grade 2) occurred in 12 patients (2.3%) and consisted of hypothyroidism, adrenal insufficiency, hypopituitarism, and 1 case each of hyperthyroidism and Cushing's syndrome. The median time to onset of moderate to severe immune-mediated endocrinopathy was 2.5 months and ranged up to 4.4 months after the initiation of ipilimumab.

Of the 21 patients with moderate to life-threatening endocrinopathy, 17 patients required long-term hormone replacement therapy including, most commonly, adrenal hormones (n=10) and thyroid hormones (n=13).

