## 6.2.2 Full Physical Exam

The investigator or qualified designee will perform a complete physical exam at screening, on C1D1 of each treatment cycle, and at discontinuation of treatment, as specified in the Study Flow Chart (Section 6.0). Clinically significant abnormal findings should be recorded as medical history.

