**Table 6 Laboratory Tests**

Hematology	Chemistry	Urinalysis	Other
Hematocrit	Albumin	Blood	Serum $\beta$ -human chorionic gonadotropin†
Hemoglobin	Alkaline phosphatase	Glucose	( $\beta$ -hCG)†
Platelet count	Alanine aminotransferase (ALT)	Protein	PT (INR)
WBC (total and differential)	Aspartate aminotransferase (AST)	Specific gravity	aPTT
Red Blood Cell Count	Lactate dehydrogenase (LDH)	Microscopic exam ( If abnormal )	Total triiodothyronine (T3)
Absolute Neutrophil Count	Carbon Dioxide ‡	results are noted	Free tyroxine (T4)
Absolute Lymphocyte Count	( $CO_2$ or bicarbonate)	Urine pregnancy test †	Thyroid stimulating hormone (TSH) PK
	Uric Acid		
	Calcium		
	Chloride		
	Glucose		
	Phosphorus		
	Potassium		
	Sodium		
	Magnesium		
	Total Bilirubin		
	Direct Bilirubin ( If total bilirubin is elevated above the upper limit of normal )		
	Total protein		
	Blood Urea Nitrogen		

† Perform on women of childbearing potential only. If urine pregnancy results cannot be confirmed as negative, a serum pregnancy test will be required.

‡ If considered standard of care in your region.

Laboratory tests for screening should be performed within 10 days prior to the first dose of treatment. After Cycle 1, pre-dose laboratory procedures can be conducted up to 72 hours prior to dosing. Results must be reviewed by the investigator or qualified designee and found to be acceptable prior to initiation of each treatment cycle.

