### 7.3.2 Events of Clinical Interest

Selected non-serious and serious adverse events are also known as Events of Clinical Interest (ECI) and must be reported within 24 hours to the Sponsor and within 2 working days to Merck Global Safety. [REDACTED]

For the time period beginning when the consent form is signed until treatment allocation/randomization, any ECI, or follow up to an ECI, that occurs to any subject must be reported within 24 hours to the Sponsor and within 2 working days to Merck Global Safety if it causes the subject to be excluded from the trial, or is the result of a protocol-specified intervention, including but not limited to washout or discontinuation of usual therapy, diet, placebo treatment or a procedure.

For the time period beginning at treatment allocation/randomization through 30 days following cessation of treatment, or until the time that a subject initiates new anticancer therapy, whichever is earlier, any ECI, or follow up to an ECI, whether or not related to Merck product, must be reported within 24 hours to the Sponsor and within 24 hours to Merck Global Safety.

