#### **Events of clinical interest for this trial include:**

1. an overdose of Merck product, as defined in Section 7.1 - Definition of an Overdose for This Protocol and Reporting of Overdose to the Sponsor, that is not associated with clinical symptoms or abnormal laboratory results.
2. an elevated AST or ALT lab value that is greater than or equal to 3X the upper limit of normal and an elevated total bilirubin lab value that is greater than or equal to 2X the upper limit of normal and, at the same time, an alkaline phosphatase lab value that is less than 2X the upper limit of normal, as determined by way of protocol-specified laboratory testing or unscheduled laboratory testing.\*

*\*Note:* These criteria are based upon available regulatory guidance documents. The purpose of the criteria is to specify a threshold of abnormal hepatic tests that may require an additional evaluation for an underlying etiology.

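### Appendix 1 schedules no blood count, chemistry or thyroid test at End of Treatment or Safety Follow-up, although adverse events, including a laboratory-defined liver event, remain reportable for up to 30 days after treatment

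*Combined protocol and SAP*

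**What the plan says.** - **Schedule.** In Appendix 1 the rows "CBC with Differential", "Comprehensive Serum Chemistry Panel" and thyroid function (T3, free T4, TSH) are marked at screening and at cycles 1 to 8, with the cycles repeating beyond 8. All three are blank at EOT and at Safety Follow-up. Adverse event review, physical examination, vital signs and ECOG are marked at Safety Follow-up but blank at EOT.
- **Timing of on-treatment samples.** Section 6.2.5, below Table 6, describes only screening and pre-dose sampling: "After Cycle 1, pre-dose laboratory procedures can be conducted up to 72 hours prior to dosing".
- **Reporting windows.** Section 7 counts an abnormal laboratory finding as a possible adverse event and has all adverse events reported for 30 days after treatment ends. For events of clinical interest (ECIs), Section 7.3.2 sets the window "through 30 days following cessation of treatment, or until the time that a subject initiates new anticancer therapy, whichever is earlier, any ECI".
- **Laboratory-defined ECI.** One ECI consists solely of AST or ALT at least 3 times the upper limit, bilirubin at least 2 times, and alkaline phosphatase below 2 times, "as determined by way of protocol-specified laboratory testing or unscheduled laboratory testing".
- **Endpoint.** Toxicity by CTCAE is a secondary endpoint (Section 2.3.2).
- **Onset.** For ipilimumab at 3 mg/kg, Section 4.2.5 reports: "The median time to onset of moderate to severe immune-mediated endocrinopathy was 2.5 months and ranged up to 4.4 months".
- **Discontinuation.** Section 6.2.2 requires the physical examination "at screening, on C1D1 of each treatment cycle, and at discontinuation of treatment". Sections 6.2.3 and 6.2.4 likewise require vital signs and ECOG at discontinuation.

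**The concern.** A reporting window is only as informative as the assessments made inside it. Here the window includes an event that can be recognised only from a blood result, and the schedule places no blood test there. Section 5.3.1 itself says that immune events may appear several months after the last dose.

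Two consequences follow. Asymptomatic liver, renal, thyroid or haematological abnormalities arising after the last dose are recorded only if someone has a reason to test, so ascertainment differs between patients. The toxicity summary, in a single-arm trial with no comparator to share the same under-ascertainment, may then come out too low.

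Separately, the EOT column of Appendix 1 does not match the text of Sections 6.2.2 to 6.2.4. Sites cannot follow both when EOT is a visit of its own.

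**Working it through.** **1. Is the blank real?** Each laboratory row has 11 cells: nine marks, then two blanks. In the same table the adverse event row ends blank then marked (EOT, Safety Follow-up), and survival status is marked in both. The columns are therefore intact, and the blanks do not look like an effect of reading the PDF.

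**2. Does other text supply a test?**
- Section 6.2.5 covers screening and pre-dose samples only.
- Section 6.3.1 asks at discontinuation for what is scheduled at the final visit, which has no laboratory mark.
- Section 6.3.4 leaves later follow-up to clinical indication.
- Section 6 and the ECI definition allow unscheduled tests but do not require them.

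**3. Length of the untested interval.**
- All treatment stops at the last infusion: 30 days from the infusion to the end of the window, or 30 + 3 = 33 days if the last sample was taken 72 hours before it.
- Assumption: cessation is counted from aspirin taken to the end of that 3-week cycle: 21 + 30 = 51 days, or 51 + 3 = 54.
- Patient stops at the next scheduled visit after pre-dose blood is drawn: that sample falls about 21 days after the last infusion. Counted from the infusion, 30 − 21 = 9 days remain.
- ECI window: it ends sooner if new anticancer therapy starts.

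**4. The protocol's onset figures, reproduced.** Section 4.2.5 reports 9 Grade 3 to 4 and 12 Grade 2 endocrinopathies. With the 511 patients given there, 9/511 = 1.8% and 12/511 = 2.3%, as stated, and 9 + 12 = 21 events, or 21/511 = 4.1%.

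**5. Last scheduled test against onset.** Study day = 1 + 21 × (cycle − 1); months = (study day − 1)/30.44.

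| Time point | Study day | Months from first dose |
|---|---|---|
| Cycle 4 sample | 64 | 63/30.44 = 2.1 |
| Median onset | about 77 | 2.5 |
| Cycle 5 sample | 85 | 84/30.44 = 2.8 |
| 30 days after cycle 4 infusion | 94 | 93/30.44 = 3.1 |
| Latest reported onset | about 135 | 4.4 |
| Cycle 8 sample | 148 | 147/30.44 = 4.8 |

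If the median covers all 21 events it is the 11th value, so at least 11 of 21 (52%) began after the planned fourth dose. The ordering holds with 28-day months (63/28 = 2.25) and with the 3-day visit window (66/30.44 = 2.2). It fails if the fourth dose is delayed a full 3 weeks (84/30.44 = 2.8).

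**6. EOT column.** Physical examination, vital signs and ECOG are required at discontinuation in Sections 6.2.2 to 6.2.4 and are blank at EOT in Appendix 1. Adverse event review is also blank there.

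**The case against.** The strongest reply is that a reader could take far more from the blank cells than they show.

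- **That no patient is ever tested after the last dose.** Footnote e of Appendix 1 provides for stopping at a scheduled visit. A patient who has pre-dose blood drawn and then stops has been tested about 3 weeks after the last infusion. A universal statement fails.
- **That day 64 is the last test for anyone who progresses at the first scan.** Section 6.2.7 puts imaging every 12 weeks, and week 12 is day 85, when cycle 5 blood is due. Appendix 1 marks the scan under cycle 4, so either reading is possible.
- **That most endocrinopathies in this trial would be missed.** Patients who continue pembrolizumab are tested at cycles 5 to 8 (days 85 to 148), beyond the 4.4-month limit. The onset figures rest on 21 events at ipilimumab 3 mg/kg, whereas this trial gives 1 mg/kg in combination. Borrowing the 4.1% rate gives 43 × 21/511 = 1.8 events in all, of which only those in early stoppers are at issue.
- **That the liver ECI cannot be detected.** Its definition accepts unscheduled results.
- **That patients who stop for toxicity are lost.** Sections 3.5 and 6.3.3 follow known events onward, and adverse event review and examination are marked at Safety Follow-up.

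All of these limits stand. None supplies a scheduled test. Follow-up of a known event does not find a new silent one, and permission to test is not uniform testing. The EOT mismatch is narrow, because EOT may be combined with Safety Follow-up, but it remains when the visits are separate.

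**Conclusion.** The point holds as a gap in scheduled ascertainment, of minor severity. Unless a patient stops at a scheduled visit with pre-dose blood already drawn, the time after the last dose has no scheduled laboratory test: at least 30 days when all treatment ends at the last infusion. The direction of any error is toward understating toxicity. Its size cannot be derived, because the documents give neither the number of patients who will stop early nor the frequency of unscheduled testing.

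The endocrinopathy timing is indicative only, and matters for patients who stop at about cycle 4 or earlier. Their last scheduled test may fall before the quoted 2.5-month median (day 64) or after it (about day 85), and in both cases before the 4.4-month upper limit. The documents do not support the inference that the toxicity endpoint is known to be biased, or that every patient has the same untested window.

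**What to change.** In Appendix 1:

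1. Mark blood count, chemistry panel and T3, free T4 and TSH at Safety Follow-up.
2. Mark the same tests at EOT when it is a separate visit and none was done in the preceding 14 days, using the non-repeat rule already in footnote e.
3. Mark adverse event review at EOT.
4. Reconcile the EOT column with Sections 6.2.2 to 6.2.4 for physical examination, vital signs and ECOG.

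The cost is one routine blood draw per patient at a visit that already exists, a small laboratory charge and an amendment to the schedule table. A separate EOT visit with no recent sample would add a second draw. No dosing or treatment rule changes.
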